4.1.3.2. Schedule B

Schedule B dose escalation is complete and the MTD is 2 mg/kg (AIBW). The modified weekly schedule will not be evaluated further in this study. In Schedule B, the starting dose of IMGN853 will be 1.1 mg/kg, which is 1/3 the 3.3 mg/kg Q3W dose level, which was deemed clinically safe in nine patients.

Patients will be enrolled in cohorts of 3 to 6 patients until the MTD is defined (Section 4.1.3.3). Planned dose levels are listed below in Table 4 and will be administered based on AIBW body weight. Based on emerging data, the CRC will decide the magnitude of the dose escalation and may determine that exploration of lower or intermediate dose levels is warranted. If at any time, the administration of IMGN853 on a weekly basis is deemed to be suboptimal or PK/ Pharmacodynamics data supports a less frequent dosing regimen, the decision may be made by the CRC to select the less frequent dosing schedule.

A patient will be deemed non-evaluable for dose escalation decisions and will not be counted toward the total cohort size if the patient did not receive a full course of treatment (i.e., all planned doses of IMGN853 for the first treatment cycle) and did not experience a DLT; or discontinued from the study prior to completing necessary safety evaluations through the end of the first cycle of treatment and did not experience a DLT. Non-evaluable patients will be replaced unless accrual to the cohort has stopped due to the occurrence of at least two patients with DLT.

ImmunoGen, Inc. Confidential Page 58 of 138

Dose Level	Dose (mg/kg)	Percent Increase From Previous Dose Level	Number of Patients (Planned)
1	1.1	N/A	3 or 4-6
2	1.8	65%	3 or 4-6
3	2.5	40%	3 or 4-6
4	3.3	32%	3 or 4-6

Table 4: Planned Dose Levels (Schedule B; Dosed by AIBW)

NOTE: If additional dose exploration is required to define the MTD then dose escalation may proceed at increments $\leq 25\%$. The CRC will determine the magnitude of the dose escalation increments following review of available clinical and PK data from patients treated in the current cohort.

4.1.3.3. Dose Escalation Rules (3+3 Design)

- If none of the 3 or 4 patients experience a DLT, then dose escalation to the next dose level will occur.
- If 1 of the initial 3 or 4 patients experiences a DLT, the cohort will be expanded to up to 6 patients. If no further DLT is seen, dose escalation to the next dose level may proceed.
- If at least 2 out of 2 to 6 patients or more than 33% of patients in any given cohort experience a DLT, the maximum administered dose (MAD) is reached, and no further dose escalation will occur. Enrollment into a cohort at lower dose level will be considered.
- Each dose level will be evaluated in a similar fashion.

The MTD is defined as the highest dose at which 1 or fewer among 6 patients or $\leq 33\%$ experiences a DLT.

Once the MTD has been exceeded, the CRC will decide whether lower dose levels should be explored further or whether an intermediate dose level should be evaluated. If additional dose exploration beyond the highest dose shown in Table 3 is required to define the MTD then dose escalation may proceed at increments specified in Table 3 and Table 4. The CRC will determine the magnitude of the dose escalation increments following review of available clinical and PK data from patients treated in the current cohort.

If there is evidence of late-occurring or cumulative DLT(s), an *ad hoc* CRC may be scheduled with participating Investigators to discuss dose level or MTD reduction. If agreed, the Investigators and Sponsor may increase the number of patients treated at a given dose level, or to enroll additional patients at the previously-completed dose level if doing so is necessary to better define the study drug's safety. Additionally, upon review of the safety data from the current cohort, the Sponsor, together with the Investigators may decide to evaluate an intermediate dose level.

4.1.4. Definition of Dose-Limiting Toxicity (DLT)

Dose limiting toxicity (DLT) will be defined as a TEAE or abnormal laboratory value related to study treatment (i.e., assessed as unrelated to disease, intercurrent illness, or concomitant medications), including those TEAEs and abnormal laboratory values that result in a failure to

ImmunoGen, Inc. Confidential Page 59 of 138

meet the criteria for re-treatment. DLTs will be considered related to the investigational agent unless there is clear evidence of an alternative explanation and this attribution is agreed to by the CRC.

For the purposes of dose escalation and determination of the MTD, only DLTs that occur during the first cycle will be necessarily considered for decisions regarding dose escalation. Clinically significant toxicities or treatment-emergent adverse events that meet the definition of dose limiting but occurring after Cycle 1 (dose modifying events) may be considered when determining the RP2D.

If a patient experiences a DLT as outlined in Table 5, the study treatment must be stopped and the toxicity (ies) in question must be followed until resolution or stabilization. If treatment is to be resumed then retreatment criteria must be met (Section 5.9.3) and administration must be resumed at a lower dose (Section 4.1.3).

Table 5: DLT Definitions

TOXICITY	DLT DEFINITION CRITERIA			
Dose delays	Failure to meet re-treatment criteria within the specified timeframe			
Hematology	CTCAE Grade 4 neutropenia ≥ 7 days.			
	• CTCAE Grade 3 or 4 neutropenia with single temperature reading ≥ 38.3°C or sustained temperature reading of > 38°C for > 1 hour			
	CTCAE Grade 3 thrombocytopenia, associated with clinically- significant bleeding that requires transfusion therapy			
	CTCAE Grade 4 thrombocytopenia			
Non-hematologic and other DLTs	• ≥ CTCAE Grade 3 nausea or vomiting despite the use of optimal anti- emetic treatments			
	• ≥ CTCAE Grade 3 diarrhea despite the use of optimal anti-diarrheal treatments			
	• Other non-hematologic toxicities of CTCAE ≥ Grade 3 except for the following:			
	AEs related to underlying disease			
	o Alopecia			
	 CTCAE Grade 3 fatigue 			
	 Lymphopenia is not considered DLT unless accompanied by clinically-significant infection 			
	 Isolated, asymptomatic Grade 3 abnormalities in biochemistry laboratory values that last for ≤ 7 days. This includes electrolyte abnormalities that respond to medical intervention. 			

For any dose limiting hepatic toxicity that does not resolve to baseline within 7 days, an abdominal CT scan must be performed to assess whether it is related to disease progression.

4.1.5. Dose Expansion Cohorts

Once the MTD is established, additional patients will be treated in a dose expansion phase that is designed to further evaluate safety and tolerability, assess preliminary efficacy at the MTD, and characterize IMGN853 Pd.

Data obtained in the dose expansion phase will help define the RP2D.

Expansion Cohort #1 will enroll 40 patients with platinum-resistant EOC, primary peritoneal cancer or fallopian tube cancer who have tumors that meet the requirement of FOLR1 positivity by IHC (\geq 25% of tumor staining at \geq 2+ intensity). The size of this cohort was increased to

ImmunoGen, Inc. Confidential Page 61 of 138

better define the frequency and assess the impact of the proposed management guidelines for ocular adverse events.

Expansion Cohort #2 will enroll 20 patients with advanced, recurrent uterine cancer; eligible patients will have tumors with an H score \geq 100 for FOLR1 expression by IHC.

Expansion Cohort #3 will enroll 20 patients with relapsed EOC; eligible patients will have tumors that meet the requirement of FOLR1 positivity by IHC ($\geq 25\%$ of tumor staining at $\geq 2+$ intensity).

Expansion Cohort #4 will enroll 20 patients with relapsed/refractory NSCLC adenocarcinoma or BAC; eligible patients will have tumors that meet the requirement of FOLR1 positivity by IHC (\geq 25% of tumor staining at \geq 1+ intensity).

Expansion Cohort #5 will enroll 40 patients with relapsed EOC, primary peritoneal cancer or fallopian tube cancer who have tumors that meet the requirement of FOLR1 positivity by IHC (\geq 25% of tumor staining at \geq 2+ intensity). Patients enrolled into this cohort will self-administer corticosteroid eye drops four times daily, for the first 10 days of each cycle, to assess whether prophylaxis with topical steroids prevents or lessens severity of ocular toxicity.

In addition to FOLR1-positivity, all patients enrolled in the expansion cohorts must meet all other eligibility criteria (Section 3.1.1). Safety will be evaluated continuously, separately, and in aggregate in the expansion cohorts. If at any time $\geq 33\%$ of patients treated in an expansion cohort experiences a Cycle 1 DLT, further enrollment to that cohort will stop and a CRC will be convened. The CRC will review all available safety data and PK data to determine how further dosing should proceed. If it is decided that a new dose should be investigated, enrollment to the cohort will begin anew.

ImmunoGen, Inc. Confidential Page 62 of 138

5. STUDY TREATMENT

5.1. Description of Study Treatment

The investigational study drug, IMGN853, will be provided by ImmunoGen, Inc. at a protein concentration of 5.0 mg/mL in an aqueous pH 5.0 buffered solution. IMGN853 will be available in a 20 mL glass vial with 20 mL deliverable volume. IMGN853 should be stored upright at 2-8°C.

5.2. IMGN853 Packaging

The IMGN853 will be provided in a 20 mL Type I glass vial. The container closure for the Type I glass vials will consist of a 20 mm ETFE-coated serum stopper (Flurotec[®]) on the top and product contact surface with a 20 mm aluminum TruEdge[®] seal with blue Flip-off[®] top. Refer to the Pharmacy Manual for labeling information.

5.3. Storage, Handling and Compatibility

Specific details regarding storage and handling can be found in the Pharmacy Manual.

All IMGN853 supplied for the study will be accompanied by accountability and shipping documents that must be maintained by the Principal Investigator or designee (e.g., the study pharmacist). The Investigator or designee must maintain an accurate record of the receipt and dispensing of IMGN853 in a drug accountability log. These records must always be available for inspection, and a copy will be supplied to ImmunoGen, Inc., on request. Information recorded on these accountability and shipping documents will include quantities received, dates and amount dispensed, the recorder's initials, patient number and initials to whom administered, lot number of drug administered, and drug lost, damaged or destroyed.

Upon completion of the study, all IMGN853 dispatched to a site must be accounted for and unused supplies destroyed according to the site's Standard Operating Procedures (SOPs). If the site cannot destroy onsite, return of unused supplies to ImmunoGen, Inc. can be arranged. The original drug reconciliation records shall be maintained at the site and a copy collected and sent to ImmunoGen once a representative of the company has confirmed the drug accountability. The pharmacy shall maintain accurate records of all study drugs that have been received, stored, dispensed, destroyed, and used. The eCRF shall also record details of IMGN853 administration such as date and time of administration.

Drug accountability will be monitored regularly.

5.4. Study Treatment Compliance

The IMGN853 supplied for the study may not be used for any purpose other than the study or administered other than as described in this protocol.

Study drug from two different drug lots cannot be mixed in a single dose administration.

Under no circumstances is the Investigator allowed to release study drug supplies to any physician not named in the Form FDA 1572 or to administer these supplies to a patient not enrolled in this study. If investigational supplies are to be dispensed from any facility other than that supervised directly by the Principal Investigator (i.e., hospital pharmacy, satellite pharmacy),

ImmunoGen, Inc. Confidential Page 63 of 138

it is the responsibility of the Principal Investigator to ensure that all study drug is maintained in the manner described.

5.5. Assignment of Patient Number

Patient numbers are assigned in sequential order as patients sign informed consent to participate.

Patients are to be registered by faxing or emailing a completed eligibility checklist and enrollment form to the Clinical Manager or designee. The checklist will be verified and a dose level will be assigned as instructed by ImmunoGen, Inc. or designee. A confirmation of registration form will be faxed or emailed back to the site to complete the registration process.

The Investigator will certify that the patient satisfies all eligibility criteria at screening and continues to satisfy all inclusion and exclusion criteria on Cycle 1, Day 1 prior to dosing.

5.5.1. Enrolled Patient Definition

Patients who receive at least one dose of IMGN853 will be considered enrolled. Patients who are issued a patient number, but who do not successfully complete the screening process and who do not receive a dose of IMGN853 will be considered a screen failure. Patient numbers for patients who screen fail will not be re-issued.

5.5.2. Patient Assignment to Dosing Schedules

Patients will be assigned to Schedule A or B based on eligibility criteria and slot availability.

5.6. Blinding

Not applicable as this is an open-label study.

5.7. Study Treatment Administration

5.7.1. Study Treatment Overview and Schedule

IMGN853 is an experimental anticancer drug, and as with other potentially toxic compounds, caution should be exercised when handling this compound. It is recommended that gloves and protective garments be worn during preparation.

5.7.1.1. Every 3-Week Schedule (Q3W)

For logistical reasons such as holidays, delays in the scheduled study treatment for up to 3 days. Additionally, shifts in the start of a new cycle by -1 or +3 days will be permitted in Cycles ≥ 3 .

5.7.1.2. Modified Weekly Schedule (Days 1, 8 and 15, Every 28 Days)

For logistical reasons such as holidays, Day 1 delays in the scheduled study treatment for up to 3 days is permitted. Additionally, shifts in the start of a new cycle by -1 or up to +3 days will be permitted in Cycles \geq 3. If patients do not meet retreatment criteria on Days 8 and 15 of a given cycle, the dose should be omitted. A delay of 1 day in the dosing of Days 8 and 15 is permitted; if a delay occurs, subsequent dosings on that cycle should be shifted by 1 day. Intervals <7 days between dosings are not permitted. The start of the next cycle should remain the same.

ImmunoGen, Inc. Confidential Page 64 of 138

5.8. IMGN853 Preparation and Administration

5.8.1. Premedication to Prevent Infusion Reaction

5.8.1.1. Schedule A

Patients should receive 10 mg IV dexamethasone, 25-50 mg diphenhydramine (IV or PO) and 325-650 mg acetaminophen (IV or PO) approximately 30 minutes prior to each infusion. If individual patients require more intensive treatment to prevent infusion reaction, investigators may modify the regimen accordingly.

5.8.1.2. Schedule B

Premedication with corticosteroids will not be employed initially. For individual patients who experience signs of infusion-related reactions, the premedication regimen outlined in Section 5.8.1.1 should be administered prior to all subsequent IMGN853 infusions. All patients dosed according to Schedule B should receive 325-650 mg of acetaminophen (PO or IV) approximately 30 minutes prior to each infusion of IMGN853 to prevent infusion-related headaches.

5.8.2. Premedication with Corticosteroid Eye Drops (Dose Expansion Cohort#5 ONLY)

All patients enrolled into Cohort Expansion 5 will be instructed to self-administer 1% prednisolone (Pred Forte[®] or generic equivalent) six times daily on Days 1-5 and four times daily on Days 6-10 of each cycle during the study (Figure 4).

[figure not shown]
These medications will be prescribed by the treating physician and will be sourced by the site. Patients will record their eye drop administration in a patient diary, which will be entered on the CRF.

5.8.3. Lubricating Eye Drops

In order to prevent dry eye, which may predispose a patient to corneal irritation, patients will be required to use preservative-free, lubricating artificial tears on a daily basis (as directed by the product label or the treating physician) for the duration of their IMGN853 treatment.

Patients in Cohort#5 will use the corticosteroid eye drops as described in Section 5.8.2 and will use the lubricating eye drops for the remainder of the cycle (Days 11 through 21 inclusive). *If patients need to use lubricating drops during Days 1-10, while steroid eye drops are being administered, they should be advised to wait at least 15 minutes following steroid administration before instilling lubricating eye drops.*

Figure 4: Co-Administration of Steroid Eye Drops and Lubricating Eye Drops (Schema)

ImmunoGen, Inc. Confidential Page 65 of 138

As with the corticosteroid eye drops, patients will record their eye drop administration in a patient diary, which will be recorded on the CRF.

5.8.4. Calculation for Adjusted Ideal Body Weight

Based on the results of the PK modeling, as described in Section 1.10.1, which suggested that dosing according to adjusted ideal body weight (AIBW) may reduce the variation in exposure within dosing cohorts, the adjusted ideal body weight calculation will be used to dose IMGN853 going forward.

The total dose of drug will be calculated based on each patient's adjusted body weight using the following formula:

Adjusted Ideal Body Weight (AIBW)

1. $IBW^1 + 0.4$ (Actual weight – IBW^1)

Where:

Ideal Body Weight (IBW)

- 1. IBW^1 (male) = $0.9H^1-88$
- 2. IBW^1 (female) = $0.9H^1-92$

(1H=height in cm; W=weight in kg)

The weight used for calculation should be obtained prior to first treatment and thereafter should only be modified for significant ($\geq 10\%$) changes in body weight (not influenced by weight gain or loss attributed to fluid retention). The desired amount should be withdrawn from the vial(s) and diluted using 5% dextrose to a final concentration as outlined in the Pharmacy Manual. **Note: IMGN853 is incompatible with saline (0.9% sodium chloride).** Therefore, dilutions should be made using 5% dextrose. Infusion bags must be labeled with the protocol number, patient number, storage temperature, dose, and volume of IMGN853 filtered into the bag, or according to institutional protocol. Once the solution is prepared, the infusion bag must not be left in direct sunlight, and the infusion must be completed within 8 hours of preparation.

Study drug from two different drug lots cannot be mixed in a single dose administration.

5.8.5. IMGN853 Administration

During the dose escalation phase, the starting dose of IMGN853 was 0.15 mg/kg for patients enrolled to Schedule A and 1.1 mg/kg for patients enrolled to Schedule B. Following Amendment 10 implementation, IMGN853 will be administered to all patients at the MTD of 6 mg/kg every three weeks. (Note: Available safety data indicate that the MTD is equal to the RP2D). IMGN853 will be administered as an IV infusion following preparation as outlined in the Pharmacy Manual. An IV tubing administration set with a 0.22 micron in-line filter must be used for infusion. Initially the study drug should be administered at a rate of 1 mg/min; after 30 minutes, the rate can be increased to 3 mg/min if well tolerated. If well tolerated after 30

ImmunoGen, Inc. Confidential Page 66 of 138

minutes at 3 mg/min, the IMGN853 infusion rate may be increased to 5mg/min. Subsequent infusions may be delivered at the tolerated rate. Therefore, the overall length of infusion will vary depending on dose and patient tolerability. Following infusion, the IV line should be flushed with 5% dextrose as needed to ensure delivery of the full dose.

Patients will be carefully observed during each infusion and vital signs taken as outlined in the Schedule of Clinical Assessments (Appendix A and Appendix B). They will remain in the clinic under observation for 4 hours after the first infusion, and for at least 1 hour after each subsequent infusion.

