All new patients enrolled in the trial will receive IMGN853 at the MTD of 6 mg/kg once every three weeks (Figure 3). Safety data available to date indicate that the MTD is equal to the RP2D. Patients currently receiving IMGN853 study treatment according to Schedule B will continue to do so.

Safety and tolerability will be further defined for the patient populations evaluated in the Dose Expansion phase of the study. The dose expansion cohorts will additionally investigate IMGN853 Pd (MTD Expansion Cohort3), preliminary anti-tumor efficacy (MTD Expansion Cohorts 1, 2 and 4), and will assess the effectiveness of primary, prophylactic steroid eye drops in preventing or lessening ocular toxicity (Cohort 5).

- a. **Expansion Cohort #1** Patients with EOC, primary peritoneal cancer or fallopian tube cancer, which is resistant to their last platinum-based therapy, excluding those patients with primary platinum refractory disease.
- b. **Expansion Cohort #2** Patients with FOLR1-positive uterine cancer that is advanced or recurrent and has received at least one platinum-based regimen, and no more than five prior systemic treatment regimens for EC

ImmunoGen, Inc. Confidential Page 35 of 138

- c. **Expansion Cohort** #3 Patients with biopsy-accessible relapsed or refractory ovarian cancer, primary peritoneal cancer or fallopian tube cancer
- d. **Expansion Cohort** #4 patients with relapsed and refractory NSCLC adenocarcinoma or BAC
- e. **Expansion Cohort** #5 Patients with EOC, primary peritoneal cancer or fallopian tube cancer, which has relapsed following platinum-based therapy, excluding those patients with primary platinum refractory disease or low grade or clear cell ovarian cancer. Patients enrolled in this cohort will be pre-treated with corticosteroid eye drops to assess whether prophylaxis with topical steroids prevents or lessens severity of keratopathy and blurred vision.

Translational research studies described above and outlined in Section 7 should provide data that will help define IMGN853's mechanism of action and help guide further clinical development.

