Schedule B, the starting dose of IMGN853 was 1.1 mg/kg, which was 1/3 the 3.3 mg/kg dose level, which was deemed clinically safe in nine patients on a Q3W schedule. All doses were calculated according to adjusted ideal body weight (AIBW). Patients were enrolled in cohorts of 3 to 6 patients and the MTD was determined to be 2.0 mg/kg (AIBW). The CRC to review safety, PK and efficacy data from the dose escalation cohorts, as well as available data from patients treated on Schedule A. The modified weekly schedule did not provide any apparent

ImmunoGen, Inc. Confidential Page 55 of 138

safety or efficacy advantage. These results were presented at the annual ASCO meeting (Borghei 2015).

Based on safety and overall response data collected through May 2015, the CRC determined that all new patients enrolled in the trial will receive IMGN853 at the MTD of 6 mg/kg once every three weeks. Safety data available to date indicate that the MTD is equal to the RP2D. Moving forward, Schedule B will not be evaluated any further in this study; however, patients enrolled to Schedule B prior to the CRC decision, will continue on this schedule.

The period of observation extends from the time the patient receives the first dose of IMGN853 until the final follow-up study visit. Patients will continue to receive IMGN853 until unacceptable toxicity or withdrawal of consent, whichever comes first, or until the Sponsor terminates the study. Patients who meet the RECIST criteria for PD while on study may remain on study, provided there is evidence of clinical benefit and no unacceptable toxicity, as agreed upon by the Investigator and the medical monitor. Patients who discontinue study drug for reasons other than PD will be followed until PD, start of new anti-cancer therapy, or death, whichever occurs first.

The primary aims of the Dose Expansion phase are to further evaluate safety and tolerability and to assess IMGN853 Pd and preliminary efficacy.

CTCAE version 4.03 will be used to grade adverse events.

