4.1.2. Cohort Review Committee

The CRC is comprised of the ImmunoGen Medical Monitor and Investigators from participating sites. Once the last patient in a given cohort has completed a cycle of study treatment, a CRC meeting will be convened to review all safety data and decide whether to continue or halt dose escalation, further expand individual dose levels to gain additional safety data, or explore lower or intermediate dose levels.

ImmunoGen, Inc. Confidential Page 56 of 138

Amendment 10 Update: The CRC convened to review safety, PK and efficacy data from the dose escalation cohorts, as well as available data from patients treated on Schedule A. The modified weekly schedule did not provide an apparent safety or efficacy advantage; moreover, while the Q3W schedule PK profile analysis indicated no accumulation of IMGN853, accumulation of IMGN853 was observed using the modified weekly schedule (Borghaei, 2015). Based on safety, PK and overall response data collected through May 2015, the CRC determined that the study will proceed with IMGN853 administered under Schedule A (Q3W) only (Figure 2). All new patients enrolled in the trial will receive IMGN853 at the MTD of 6 mg/kg once every three weeks. Safety data available to date indicate that the MTD is equal to the RP2D. Patients currently being treated using Schedule B will continue to be dosed according to this schedule.

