5.9.1.2. To Continue Treatment within a Cycle- Schedule B (modified weekly)

Amendment 10 Update: Following completion of the Schedule B Dose Escalation portion of the study, the CRC reviewed safety, PK and efficacy data from both dosing schedules and based this review, made the decision to discontinue further investigation of Schedule B dosing. While patients currently receiving IMGN853 study treatment according to Schedule B will continue to do so, new patients enrolled to the study will receive treatment according to Schedule A only.

In the absence of otherwise dose-limiting toxicity, for a patient to continue treatment within a cycle, the following criteria must be met.

- ANC must be $\geq 1.0 \times 10^9 / L (1,000 / \mu L)$
- Platelet count must be $\ge 75 \times 10^9 / L (75,000 / \mu L)$
- All non-hematologic toxicities for which a causal association to study treatment cannot be ruled out, must be ≤ Grade 2 (except alopecia) or returned to baseline; the exception to this rule is treatment-emergent eye disorders, which must have recovered to ≤ Grade 1 or baseline
- A minimum of 7 days (~168 hours) must have elapsed between IMGN853 doses

If the patient does not meet these criteria, dosing will be delayed and the patient should be reevaluated within 72 hours. Dosing may resume if these criteria have been met. If the criteria are not met due to insufficient recovery from a treatment-related toxicity, then that week's dose will be considered "missed".

The use of granulocyte growth factors in accordance with ASCO guidelines may be implemented at the discretion of the treating physician after Cycle 1.

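### Protocol Section 5.8.5 puts all patients on 6 mg/kg every three weeks after Amendment 10, although four other sections reserve Schedule A for new patients and keep ongoing Schedule B patients on Schedule B

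*Protocol*

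**What the plan says.** Section 5.8.5 first gives the escalation starting doses for Schedule A and Schedule B and then states: "Following Amendment 10 implementation, IMGN853 will be administered to all patients at the MTD of 6 mg/kg every three weeks". No exception follows.

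Other current sections state a narrower rule:

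- **Section 1.7:** "All new patients enrolled in the trial will receive IMGN853 at the MTD of 6 mg/kg once every three weeks", and then "Patients currently receiving IMGN853 study treatment according to Schedule B will continue to do so".
- **Section 4.1.1:** "all new patients enrolled in the trial will receive IMGN853 at the MTD of 6 mg/kg once every three weeks", while "patients enrolled to Schedule B prior to the CRC decision, will continue on this schedule".
- **Section 4.1.2:** the same regimen, again for new patients only, and "Patients currently being treated using Schedule B will continue to be dosed according to this schedule".
- **Section 5.9.1.2:** "new patients enrolled to the study will receive treatment according to Schedule A only". It also keeps current Schedule B patients where they are. It does not name the 6 mg/kg dose.

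The synopsis likewise limits the 6 mg/kg regimen to new patients. None of this is amendment-log text. All of it is current, and Section 5.8.5 itself refers to Amendment 10 by name.

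**The concern.** Two rules apply to the same people. A patient on Schedule B when Amendment 10 took effect stays on Days 1, 8 and 15 of a 28-day cycle under four sections, but moves to 6 mg/kg every three weeks under Section 5.8.5. The second rule sits in the section that sets infusion rate, in-line filter and observation time, which is where site staff would look for dosing instructions.

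If the sentence were followed literally, the size of a single infusion is what would matter most. Section 1.10.1 reports that higher Cmax values correlated with treatment-emergent eye disorders, and Section 1.10.2 explains that the modified weekly schedule was explored in order to hold Cmax down. Premedication also differs: Section 5.8.1.1 calls for dexamethasone before each Schedule A infusion, whereas Section 5.8.1.2 does not use corticosteroids initially on Schedule B. The protocol appears to contain no rule for moving a patient from one schedule to the other.

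**Working it through.** The plan gives no figure to reproduce here. The check compares the text and then uses simple arithmetic to show the size of the discrepancy.

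**1. Which rule is the intended one?**

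| Place in the protocol | Who receives the stated regimen after Amendment 10 | Ongoing Schedule B patients |
|---|---|---|
| 5.8.5 | all patients (6 mg/kg Q3W) | no exception stated |
| 1.7 | new patients (6 mg/kg Q3W) | stay on Schedule B |
| 4.1.1 | new patients (6 mg/kg Q3W) | stay on Schedule B |
| 4.1.2 | new patients (6 mg/kg Q3W) | stay on Schedule B |
| 5.9.1.2 | new patients (Schedule A, dose not named) | stay on Schedule B |

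The protocol also keeps working instructions for Schedule B. Section 5.7.1.2 still sets within-cycle windows ("A delay of 1 day in the dosing of Days 8 and 15 is permitted"). Section 5.8.1.2 gives Schedule B premedication, Section 5.9.1.2 gives within-cycle retreatment criteria, and Table 11 gives reductions from 2.0 and 1.8 mg/kg. Those provisions would serve nobody if every patient had moved to Schedule A. The wording of 5.8.5 is therefore the error.

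**2. Size of the discrepancy under a literal reading**

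Inputs:
- Section 5.8.5: 6 mg/kg every 3 weeks.
- Section 4.1.3.2: Schedule B MTD of 2 mg/kg, and Table 4 planned levels of 1.1, 1.8, 2.5 and 3.3 mg/kg.
- Section 4.1.1: Schedule B given on Days 1, 8 and 15 of 28, so 3 doses per 4 weeks.
- All doses are per kg of adjusted ideal body weight (AIBW).

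Formulas, with *d* the Schedule B dose:
- Weekly dose at 6 mg/kg Q3W = 6 / 3 = 2.0 mg/kg/week
- Weekly dose on Schedule B = 3*d* / 4
- Single-infusion ratio = 6 / *d*
- Weekly ratio = 2.0 / (3*d* / 4)

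At *d* = 2.0, Schedule B delivers 3 × 2.0 / 4 = 1.5 mg/kg/week. The single-infusion ratio is 6 / 2.0 = 3.0 and the weekly ratio is 2.0 / 1.5 = 1.33, which is +33%.

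The documents do not state which doses ongoing Schedule B patients were receiving. **Assumption:** any Table 4 level or the stated MTD.

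| Schedule B dose (mg/kg) | Weekly dose (mg/kg) | Single-infusion ratio | Weekly change |
|---|---|---|---|
| 1.1 | 0.825 | 5.5 | +142% |
| 1.8 | 1.35 | 3.3 | +48% |
| 2.0 | 1.5 | 3.0 | +33% |
| 2.5 | 1.875 | 2.4 | +7% |
| 3.3 | 2.475 | 1.8 | −19% |

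The weekly doses are equal at *d* = 2.0 × 4 / 3 = 2.67 mg/kg. The single infusion is larger at every dose in the table.

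**The case against.** The strongest counter-argument is that the sentence is loose and would not mislead. It follows one about starting doses for patients enrolled to each schedule, so it can be taken to mean the dose for anyone enrolled from then on. Section 5.8.5 still points to Appendix B, the Schedule B assessment schedule, for vital signs. A fully literal reading would also override the Schedule A reductions in Table 11 and the requirement in Section 5.9.4.2 to stay at a reduced dose, which nobody can have intended. The sponsor assigns the dose level at registration (Section 5.5). These points stand as evidence of intent and limit the weight of the finding. They do not change what the sentence says.

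The safety argument also needs context. The dose is 6 mg/kg by AIBW every three weeks, the declared Schedule A MTD, which the protocol equates with the recommended Phase 2 dose and gives to every new patient. The Cmax association came from total-body-weight dosing, and Section 1.10.1 predicts less ocular toxicity with AIBW. A threefold larger infusion may still raise Cmax, but the regimen is not an untested one.

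There are two fair limits on the numbers. The 2.5 and 3.3 mg/kg rows are planned levels above the stated MTD, Table 11 has no reductions from them, and nothing shows that an ongoing patient was receiving either. The negative weekly change depends wholly on the 3.3 row. In addition, Section 1.1 of the SAP says that Schedule B stopped before an MTD was identified, whereas the protocol gives 2.0 mg/kg. The 3.0-fold and 33% figures hold for a 2.0 mg/kg dose whatever it is called.

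**Conclusion.** The concern holds. Section 5.8.5 is wrong as written for patients still on Schedule B, because it omits the restriction to new patients and the exception that the other sections state. The error is minor: the correct rule appears several times elsewhere, the documents do not show that a site would follow the faulty sentence, and sample size and analyses are untouched.

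The dosing consequence is conditional on a literal reading. The best-supported illustration is the 2.0 mg/kg case. The wider range rests on the assumption about ongoing doses set out above. No count of affected patients can be given, because the number remaining on Schedule B is not stated.

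**What to change.** In Section 5.8.5, restrict the post-Amendment 10 sentence to newly enrolled patients, and add that patients already receiving Schedule B remain on that schedule. The sponsor should also confirm what wording applies to ongoing Schedule A escalation patients, because the sections cited here do not address them.

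This costs one sentence in a protocol clarification or the next amendment. It adds no patients, procedures or analyses.
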